6.2.2 Enrollment, Baseline, and/or Randomization

Enrollment

Enrollment is defined as the date of randomization at which point all eligibility criteria are confirmed and the individual has agreed to participate; this is recorded on a case-report form. AEs will be collected after the participant is enrolled. Participants will be told to contact study staff and/or providers about any health related changes they experience. See Safety Assessments and the DSMP for additional details.

Baseline Assessments

For participants who have successfully been screened for eligibility and are enrolled into the study, baseline assessments are performed against which to measure the study outcome. These will also ensure the groups are balanced with respect to baseline characteristics.

Primary and secondary outcomes will be measured using web-based, self-report questionnaires administered free of provider and investigator influence.

Baseline characteristics

Important baseline characteristics (e.g., demographics, past healthcare use, COVID-19 impact¹⁹⁰, LBP duration, prior episodes of LBP, visual trajectory questionnaire for pain¹⁸⁶, Quebec Task Force classification of spinal disorders¹³³) will be collected through web-based, self-report questionnaires and the screening provider's medical history and physical exam. Baseline measures included in the NIH research task force's minimum dataset will be collected.⁷³

Primary Outcome Measures

The following primary outcome measures will be collected during the baseline assessment.

- Low back pain impact is defined as a combination of pain intensity, pain interference with normal activities, and functional status, using 9 items of the 29-item PROMIS short form. These items have substantial research support to validate their discriminatory and prognostic importance. Scores on the 9 PROMIS-based items yielding Impact Stratification range from 8 (least impact) to 50 (greatest impact).¹⁹¹
- LBP Intensity: participants will be asked to rate their average LBP over the last week on an ordinal 11-box NRS (0=no LBP, 10=the worst LBP possible). Several studies have shown that ordinal pain scale measures perform as well as the 10-cm Visual Analog Scale (VAS),¹³⁴ a simple, frequently used valid assessment of variation in pain intensity^{119 135} and a reliable measure of treatment efficacy.¹³⁶ The advantage of the 11-box scale over the VAS is that it is easier to administer and score.¹¹⁹
- Low back disability will be measured with the modified Roland Morris Disability Questionnaire, a 24-item questionnaire that measures the degree to which the low back problem or leg pain restricts patients' daily activities. It has a high level of internal consistency, construct validity, and responsiveness.¹²⁰

Secondary Outcome Measures

- The PROMIS-29 Profile v2.0 Instrument (www.nihpromis.org) as recommended by the NIH RTF will be used with the exception of the question on pain intensity which is collected elsewhere on a weekly basis.⁷³ This includes the following measures: pain interference with normal activities, physical function, anxiety, depression, fatigue, sleep disturbance and the ability to participate in social roles and activities.

- LBP frequency will be collected by asking participants to report the number of days LBP has been a problem in the past 7 days.⁷³
- OTC and prescription medication use for LBP, including class and frequency by class.
- Health care utilization including provider visits, ER visits, MRIs, injections, hospitalizations, and surgeries.
- Productivity loss related to LBP (e.g., missed work, reduced productivity while at work) will be assessed using questions from the Institute for Medical Technology Assessment's productivity cost questionnaire.¹³⁷
- Physical exam objective outcome measures including QTF classification¹³³, timed up and go test, 5 times sit-to-stand test^{185, 187, 188}, and the sock test.¹⁸⁵
- Chronic interference with daily activities assessed using “how often has low-back pain interfered with your ability to do regular activities over the past 6 months?” on a 3-item scale (less than half the days in the past 6 months, at least half the days in the past 6 months, every day or nearly every day in the past 6 months).
- Prevention of cLBP at 6 and 12 months, as measured by the proportion of patients in each group meeting the definition by the NIH Task Force on Research Standards for Chronic LBP (i.e., ongoing low back problem on $\geq 50\%$ of days over past 6 months).

Psychosocial Mediator Measures

- Self-efficacy will be assessed using the 22-item Chronic Pain Self-Efficacy Scale that will be adapted for acute/sub-acute pain.¹³⁸
- Coping will be assessed using an adapted version of the 28-item Brief COPE instrument.¹³⁹
- Kinesiophobia will be measured using the 11-item Tampa Scale for Kinesiophobia demonstrated to have internal consistency, responsiveness and validity similar to the original 17-item instrument.¹⁴⁰
- Catastrophizing (Pain Catastrophizing Scale¹⁴¹) is measured using the 13-item Pain Catastrophizing Scale; it uses a 5-item point scale (0=not at all, 4 all the time) and has internal consistency and validity.
- Measurement of key non-specific factors that may influence outcomes will be measured using the short forms for positive outlook (6-item) from the Healing Encounters and Attitudes Lists (HEAL)

Randomization

Randomization will precede intervention administration. Randomization will occur within 7 business days of finalizing eligibility determination. Persons who are not randomized within this time frame will repeat the in-person/videoconference screening. Interventions will be initiated within 7 business days of randomization/ enrollment.

6.2.3 Blinding

Blinded Personnel:

Blinding of treatment providers and participants is not feasible. However, the following steps will be taken to minimize potential bias and enhance study rigor:

- a). all study personnel involved in screening and enrollment will be masked to upcoming randomization assignments;
- b). all study personnel involved in outcome assessment will be independent of intervention delivery, and trained in ensuring unbiased data collection and blinded to study assignment until database is locked;
- c). only a single member from the DCC will be unblinded and have access to treatment group assignment for the purpose of creating closed DSMB reports; and
- d). participants will be queried in self-report questionnaires as to whether or not anybody attempted to influence their responses.

6.2.4 Follow-up Visits

Intervention Visits

The following information will be collected at each intervention visit, which will occur as needed throughout the one year as there is no set schedule of treatments:

- Treatment delivery format – in-person, videoconference or phone
- Treatment administered – provider's record treatment administered including required, allowed and prohibited treatments to assess treatment fidelity and adherence. (Clinical notes will be documented in the medical record as required for patient management and for compliance with provider licensing requirements).
- Adverse events (AEs) - participants will be asked about the occurrence of AE/SAEs by their treatment provider at each visit. The AE protocol described in section 7, Safety and Assessments will be initiated and adhered to for all AEs identified.

Weekly Follow-up

Weekly outcomes will be collected electronically via direct patient self-report; participants who are unable to provide electronic data will be contacted directly by blinded study staff who will ascertain outcomes. Additional information related to data collection and quality assurance is described in section 10.

The following outcomes will be collected on a weekly basis for one year (\pm 2 days):

- Primary outcomes
 - Pain intensity
- Secondary outcomes
 - LBP frequency

Monthly Follow-up

Monthly follow-up data (Months 1-12) will be collected electronically via direct patient self-report. Participants who are unable to provide electronic data will be contacted directly by blinded study staff who will ascertain outcomes, or they will be mailed a paper copy of the questionnaire to complete and return to the study team. Additional information related to data collection and quality assurance is described in section 10.

The following outcomes will be collected on a monthly basis for one year (\pm 7 days):

- Primary outcomes
 - Disability - Roland Morris Disability Questionnaire
 - Low Back Pain Impact - subset of PROMIS-29
- Secondary outcomes
 - PROMIS measures, additional healthcare use, medication use, and productivity loss
 - AEs -participants will be queried about AEs associated with study interventions (e.g., increased pain, neurological symptoms, medication side effects etc.).^{11 142}
¹⁴³ The AE protocol described in section 7, Safety and Assessments will be initiated and adhered to for all AEs identified.

Week 2 Follow-up

In addition to outcomes collected weekly, the following outcomes will be collected at week 2 (\pm 7 days)

- Psychosocial mediator measures
 - Measurement of key non-specific factors that may influence outcomes will be measured using the short forms for patient-provider connection (7-item), healthcare environment (6-item), and treatment expectancy (6-item) from the Healing Encounters and Attitudes Lists (HEAL)

Month 1 Follow-up

In addition to outcomes collected weekly and monthly, the following outcomes will be collected at month 1 (between -7 and +14 days)

- Psychosocial mediator measures
 - Measurement of key non-specific factors that may influence outcomes will be measured using the short forms for patient-provider connection (7-item), healthcare environment (6-item), treatment expectancy (6-item), and positive outlook (6-item) from the Healing Encounters and Attitudes Lists (HEAL)
- Intervention uptake (SSM, SSM + SMT participants only)
 - To measure patient's use of recommended activities we will document in patient self-report questionnaires the use of the main SSM components using the following question: How many days in the past week did you use: the mind-body skills (like relaxed breathing, progressive muscle relaxation) recommended by your provider; the exercises recommended by your provider; the postural awareness suggestions (like neutral spine) recommended by your provider; other

- tips recommended by your provider (like suggestions for sleep, communicating with others, etc.); the workbook.
- Telehealth Usability Questionnaire (TUQ)

Month 2 Follow-up

In addition to outcomes collected weekly and monthly, the following outcomes will be collected at month 2 (between -7 and +14 days)

- Low back physical exam objective outcome measures
- Secondary outcomes
 - Patient satisfaction will be measured using a 7-point Likert scale (from completely satisfied to completely dissatisfied).¹⁴⁴
 - Global improvement will be measured using a 9-point scale ranging from completely recovered to vastly worse.¹⁴⁵
 - SBST status
- Psychosocial mediator measures
 - Measurement of key non-specific factors that may influence outcomes will be measured using the short forms for positive outlook (6-item) from the Healing Encounters and Attitudes Lists (HEAL) .
 - Self-efficacy, Coping, Kinesiophobia, Pain Catastrophizing
- Intervention uptake (SSM, SSM + SMT participants only)
- COVID-19 impact & Telehealth Usability Questionnaire (TUQ)

Month 6 Follow-up

In addition to outcomes collected weekly and monthly, the following outcomes will be collected at month 6 (between -7 and +14 days)

- Secondary outcomes
 - Satisfaction, global improvement, chronic interference with daily activities and SBST status
 - Prevention of cLBP will be measured using the NIH RTF definition of cLBP “a back pain problem that has persisted at least 3 months and has resulted in pain on at least half of the days in the past 6 months.” Specifically, this will be assessed with NIH RTF minimum dataset items 1 (LBP duration) and 2 (proportion of days that LBP has been a problem over the past 6 months).⁷³
- Intervention uptake (SSM, SSM+SMT participants only)
- Psychosocial mediator measures
 - Self-efficacy, Coping, Kinesiophobia, Pain Catastrophizing, and HEAL positive outlook measure.
- COVID-19 impact

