5. STUDY INTERVENTIONS

Patients will be randomized to one of the following treatment groups within the 2x2 factorial design: (1) SMT, (2) SSM, (3) the combination of SMT+SSM, or (4) MC. The initial treatment period is 8 weeks. Decisions regarding visit frequency will be made collaboratively by the provider and patient, as is typical in real-world settings. Participants will be required to attend 75% of prescribed intervention visits to be considered compliant over the 8-week period. In addition, participants have the option to receive additional treatment in the group to which they were randomized if they experience a recurrence of an acute LBP episode during the 10 month follow-up period. This additional treatment will occur in the same study clinic, or virtually using HIPAA compliant Zoom, with the same provider when possible. Participants will not be offered the option to receive treatment delivered in any of the other 3 study groups.

The primary goal of SMT is to address the biological and physical aspects of LBP (e.g., spinal dysfunction) with the intention of restoring maximum movement and functional ability of the spine. The goals of SSM are to primarily address the psychosocial aspects of acute and sub-acute LBP, by providing patients' the opportunities to develop their capacity and motivation to self-manage their LBP in an adaptive manner.^{45 108} The goals of the MC group will be to provide care for acute and subacute LBP as it would typically be delivered in primary care settings.

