6. STUDY PROCEDURES

6.1 Schedule of Evaluations

See Table on next page

Assessment	Initial Screen	Baseline/ Enrollment (Day 0)	Intervention Visits (Months 0-2)	Weekly Follow-Up (Weeks 1-52)	Follow-Up (Week 2)	Monthly Follow-Up (Months 1-12)	Follow-Up (Month 1)	Follow-Up (Month 2)	Follow-Up (Month 6)	Follow-Up (Month 12)
Informed Consent	x	x								
Demographics	x	x								
Medical History & Current Medications		x								
Physical Exam including objective outcomes		x						x		
Inclusion/Exclusion	x	x								
Technology Assessment**		x								
COVID -19 Impact		x						x	x	x
TUQ**		x					x	x		
STarT Back Screening Tool Status	x							x	x	x
Chronic LBP status (NIH RTF definition)	x	x							x	x
Chronic interference with daily activities	x	x							x	x
LBP intensity	x	x		x						
LBP frequency		x		x						
Pain Trajectory		x								x
Implementation Measures	x	x						x	x	x
Randomization/Enrollment		x								
Treatment Administered (booster sessions allowable in months 3-12)			x							

Intervention Uptake							x	x	x	x
Disability, PROMIS, healthcare and medication use, and productivity loss		x				x				
Adverse events*		x	x			x				
Satisfaction and global improvement								x	x	x
Non-specific factors (HEAL)		x			x		x	x	x	x
Psychosocial Mediators (self-efficacy, coping, kinesiophobia, and pain catastrophizing)		x						x	x	x
Participant Close Out										x

*Participants can also report adverse events to the PI's or study staff at any point during the trial
 ** Technology Assessment and the Telehealth Usability Questionnaire (TUQ) will be administered to participants who are enrolled in the 2-arm study only. Technology Assessment and the Telehealth Usability Questionnaire (TUQ) may be administered to participants in the 4-arm study if applicable (e.g., if screening and/or treatments are done virtually).

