7. SAFETY ASSESSMENTS

7.1 Specification of Safety Parameters

Following enrollment, participants will be asked about the occurrence of AE/SAEs by their treatment provider at every visit. In addition, participants will be informed to report AE/SAEs directly to study staff throughout the study period and will also be asked if they experienced any AE/SAEs associated with study interventions on monthly self-report surveys. Events will be followed for outcome information until resolution or stabilization. The PI or designee will record all reportable events with start dates occurring any time after enrollment until 7 (for non-serious AEs) or 30 days (for SAEs) after the last day of study participation.

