7.3 Adverse Events (AEs) and Serious Adverse Events (SAEs)

AE is generally defined as any unfavorable and unintended diagnosis, symptom, sign (including an abnormal laboratory finding), syndrome or disease which either occurs during the study, having been absent at baseline, or if present at baseline, appears to worsen. AEs are to be recorded regardless of their relationship to the study intervention.

The following scale will be used to grade AEs:

1. Mild: no intervention required; no impact on activities of daily living (ADL).
2. Moderate: minimal, local, or non-invasive intervention indicated; moderate impact on ADL.
3. Severe: significant symptoms requiring invasive intervention; subject seeks medical attention, needs major assistance with ADL.

We will measure and compare rates of AEs across the four treatment arms. We will specifically look for common treatment-related AEs that include: LBP, soreness at the treatment site, gastrointestinal symptoms, emotional discomfort, and other events. We will capture AEs prospectively from study participants through monthly surveys and at in-person/videoconference/telephone visits. Each unique occurrence will receive a separate ID in order to avoid duplication in documentation.

[figure not shown]
SAE is generally defined as any untoward medical occurrence that results in death, is life threatening, requires inpatient hospitalization or prolongation of existing hospitalization, results in persistent or significant disability/incapacity, or is a congenital anomaly or birth defect.

We will collect SAEs both passively through ad hoc reporting and through systematic evaluation at study visits. Given the nature of the interventions we do not anticipate any specific treatment-related SAEs and therefore focus on standard and LBP-specific serious events: death; severe or permanent disabilities; life-threatening conditions; hospitalizations; other important medical events; progressive neurological deficits, or cauda equina syndrome.

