7.5 Follow-up for Adverse Events

AEs/SAEs will be identified during the intervention phase at study visits and during the study follow-up phase using monthly self-report questionnaires (surveys) or through direct contact with study staff. Events will be followed until resolution or stabilization, whichever occurs first; resolution and stabilization will be determined by the PI with input from the study clinician when appropriate.

If an AE/SAE occurs during the intervention phase, the study clinician will monitor the AE/SAE while the participant is under their care, this will include a medical evaluation and treatment, or modifications to treatment as necessary to protect the participant and minimize harm. If warranted, referral to an outside provider will be made.

If an AE/SAE occurs during the follow-up phase, study staff will be in regular contact with the participant as the event permits.

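### The monthly survey asks only about intervention-associated adverse events, so other events after week 8 are not systematically solicited unless a booster visit occurs

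*Combined protocol and SAP*

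**What the plan says.** **The rule.** Section 7.3 of the protocol states that "AEs are to be recorded regardless of their relationship to the study intervention". The same section plans a comparison of AE rates across the four arms, and section 9 lists AEs among the secondary outcomes compared with medical care (MC).

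**The monthly question.** Section 6.2.4 (Monthly Follow-up) says that "participants will be queried about AEs associated with study interventions (e.g., increased pain, neurological symptoms, medication side effects etc". Section 7.1 says that participants "will also be asked if they experienced any AE/SAEs associated with study interventions on monthly self-report surveys". The restriction therefore appears in two places and covers serious events as well.

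**Where events are found.** Section 7.5 has events identified at study visits in the intervention phase and, later, "during the study follow-up phase using monthly self-report questionnaires (surveys) or through direct contact with study staff".

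**Visits.** Section 5 says: "The initial treatment period is 8 weeks". After that, the schedule in section 6.1 describes "booster sessions allowable in months 3-12", which depend on a recurrence. When a visit does take place, "participants will be asked about the occurrence of AE/SAEs by their treatment provider at each visit" (section 6.2.4), with no limit on relationship.

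**Related data.** Section 6.2.2 lists as a secondary outcome "Health care utilization including provider visits, ER visits, MRIs, injections, hospitalizations, and surgeries", and section 6.2.4 has healthcare use collected monthly.

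**The concern.** The recording rule covers all causes, but the scheduled question that serves it for most of the year is narrower. If the plan is followed as written, an event in month 7 that is not regarded as intervention-associated is not asked about, unless the participant happens to have a booster visit.

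Two things are at stake. The first is completeness of all-cause AE and SAE records in follow-up. Section 7.3 anticipates no specific treatment-related SAEs and so directs attention to standard serious events such as death and hospitalisation. A question restricted to intervention-associated events suits that target poorly.

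The second is the comparison between arms. Participants know their treatment, and the unrestricted inquiry happens only at visits, whose number differs by arm. The monthly survey is the one scheduled inquiry that runs at equal frequency in every arm, and it is the one that carries the restriction.

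**Working it through.** The plan gives no AE rate that depends on this point, so there is no figure to reproduce. The check sets the provisions side by side.

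**Step 1: which AE inquiries are scheduled.** The AE row in section 6.1 is marked at baseline, at intervention visits and at monthly follow-up. It has no separate mark at months 2, 6 or 12.

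**Step 2: what each route covers after month 2.**

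| Route | Scheduled in months 3-12? | Limited to intervention-associated events? |
|---|---|---|
| Monthly survey (6.2.4, 7.1) | Yes, every month | Yes |
| Provider inquiry at visits (6.2.4, 7.1) | Only if a booster visit occurs | No |
| Participant contacts staff (6.1 footnote, 6.2.2, 7.1) | No, spontaneous | No |
| Ad hoc SAE reports (7.3) | No, spontaneous | No |

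No row is both scheduled for everyone and unrestricted.

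**Step 3: length of the affected period.** Follow-up is 12 months and the initial treatment period is 8 weeks, shown as months 0-2 in the schedule. For a participant without booster visits, 12 − 2 = 10 months have the restricted survey as the only scheduled AE inquiry.

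**Step 4: unequal visit inquiry.** Section 5.4 anticipates 4-6 visits for most participants receiving spinal manipulation (SMT), 4-8 for supported self-management (SSM) and 2-4 for MC. Opportunities for unrestricted inquiry therefore differ by arm even within the first 8 weeks. Booster visits may add to the difference later, but the documents give no expected number.

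**Step 5: size.** The number of events left to spontaneous report is the number of participants without booster visits, times the event rate in months 3-12, times the share of events falling outside the question. The documents give none of these three quantities, so I give no count.

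**Step 6: a possible safety net.** The monthly healthcare-use items could reveal serious events. Nothing in the text I have says that an answer to them opens an AE or SAE record. I could not see the reporting figure in section 7.4 or the Data Safety Monitoring Plan listed in section 15, so such a link may exist there.

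**The case against.** **Unattributed events are not simply lost.** A reader might infer that every such event in months 3-12 is missed. The documents do not support that. Section 6.2.2 has participants told to contact staff or providers about any change in health, the footnote in section 6.1 allows reports at any time, section 7.1 asks for direct reports throughout, and providers ask at any booster visit. This stands. The supportable claim is that these events are not systematically solicited.

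**The participant may not be the one judging cause.** A reader might also infer that the form makes an unblinded participant decide causality. The form is not in the documents. The examples in section 6.2.4, the expected-event lists in section 7.2 and the list of common treatment-related events in section 7.3 would fit a symptom checklist that asks for no attribution. This stands too. A checklist of intervention-type symptoms would still not ask about an unrelated hospitalisation, however, so the gap in solicitation remains.

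**Recording is not soliciting.** Section 7.3 can be read as requiring that whatever comes to light be recorded, and it says openly that SAEs are collected partly by passive report. On that reading there is no strict contradiction. But the section also plans a between-arm comparison of rates, and rates need comparable ascertainment, which spontaneous report does not secure.

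**Halting guidance.** A reader might extend the point to section 7.6. That guidance counts only unexpected, related events, so truly unrelated events cannot affect it. It would suffer only if the form asks for attribution and a related event goes unrecognised, which is not documented.

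**Direction.** The documents do not establish which arm would be under-counted more. Section 7.2 lists expected events for SSM as well as for SMT and MC.

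**Conclusion.** The point holds in a limited form. Sections 6.2.4 and 7.1 are narrower than the recording rule and the four-arm comparison in section 7.3. For participants without booster visits, events not linked to the intervention are not systematically solicited for about 10 of 12 months and rest on spontaneous report. Under-ascertainment is likely, and a difference by arm is possible.

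This rests on two assumptions: that the survey follows the wording of sections 6.2.4 and 7.1, and that spontaneous report is less complete than direct inquiry. The amount of under-ascertainment and its direction by arm cannot be derived from the documents. The primary effectiveness analyses are not affected.

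**What to change.** 1. Reconcile sections 6.2.4 and 7.1 with section 7.3. Have the monthly survey ask about any new or worsened health problem since the last survey, with relatedness judged afterwards by the investigator.
2. Use monthly reports of hospitalisation, emergency visits or surgery to prompt AE/SAE follow-up. First confirm the scope of those items: section 6.2.2 does not say whether they cover all causes, and the neighbouring items on medication and productivity are specific to back pain. The prompt helps only as far as the items are not so limited.
3. Report investigator-judged related events and all-cause events separately by arm, and show counts before and after the change separately.
4. If the survey can no longer be changed, state that unrelated AEs in follow-up rest on spontaneous report, and limit the between-arm AE conclusion accordingly.

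The cost is one reworded item, one automated flag, more unrelated events for sites to process, and a break in the AE series at the date of change. The data coordinating centre already plans automated alerts (section 5.4) and logic-based data checks (section 10.3.5), so the flag should add little.
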